Human Oral Microbe Identification using Next Generation Sequencing (HOMINGS) utilizes the speed and efficiency of next generation sequencing combined with the refinement of species-level identification. Nearly 600 oral bacterial taxa are identified at the Species-level and Genus-level identification of remaining sequences for 129 genera. HOMINGS allows identification and comparison of bacterial associations in oral health and disease, including different types of periodontitis, caries, gingivitis, ventilator-associated pneumonia, endodontic and odontogenic lesions, abscesses, and halitosis. Also, HOMINGS can determine the efficacy of therapies/treatments, e.g., mouth rinses, antibiotic treatment, scaling and root planning, and laser or periodontal surgery. HOMINGS will be utilized for microbial analysis in this study.

Research Question:

What is the mechanism of action of silver diamine fluoride (SDF) on bacteria involved in root or cervical carious lesions using human oral microbe identification microarray (HOMINGS) technology?

Objective:

To **assess** the effect of SDF treatment on a large array of microorganisms present in root or cervical carious lesions using HOMINGS technology. This will be accomplished by assessing microbial deposits on root or cervical caries lesions before and 1 month after SDF application.

Rationale:

Older people that have caries-active disease experience root caries at a rate which is at least as great as that of coronal caries among adolescents.²⁷

The use of fluoride releasing agents as a means of preventing dental caries has long been recognized, and amongst these agents silver diamine fluoride (SDF) has received considerable attention as a caries-arresting agent of choice.²⁸

Silver diamine fluoride outperforms other anticaries medicaments such as chlorhexine, NaOCl-based gel (Carisolv), and an enzyme-based gel (Papacarie) in killing cariogenic bacteria in dentinal tubules, and results in less aversive taste and texture responses than to fluoride varnish.²⁹

38% SDF arrests dental caries producing bacteria such as *Streptococcus mutans*, *Streptococcus sobrinus*, *Lactobacillus acidophilus*, *Lactobacillus rhamnosus* and *Actinomyces naeslundii* by reducing the demineralization process. It minimizes the loss of mineral content and slows down collagen I

destruction. Furthermore, it contains high concentrations of silver and fluoride ions, which may inhibit the growth of multi-species cariogenic biofilms.¹⁰

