Eligible study subjects will have plaque collected from 1 randomly selected caries lesion that meets the inclusion criteria. Before applications of the study agent, a piece of gauze will be used to dry the teeth. Bacterial samples from subjects' root or cervical carious lesions will be collected with sterile Gracey curettes via a gentle scraping movement.^{34,35} Samples will be collected at the beginning of each appointment, but following consent and eligibility review. Samples will be frozen until analyses. The SDF solution will then be applied onto the exposed root surfaces of participants by means of a disposable microbrush following the manufacturer's recommendation by using their specialized Advantage Arrest applicator. The applicator will not absorb the product as it applies, and there is no risk of leaving flock portions of the applicator on the site. The surface tension of the material being applied holds the liquid on the applicator until it contacts the application site. The participants will be instructed not to eat or drink for one hour after treatment. Patients will be asked to return 1 month later. At this time, the lesions will be assessed for changes in hardness and color, and then a second microbial sample will be collected as described below and frozen until analyses.

Sample Size:

A sample including 20 subjects is decided to constitute the study sample. Samples will be collected from each patient at the first visit and at the one month recall visit.

An additional 2 test plaque samples will be collected for calibration purposes. These will be collected either from subjects who will also participate in the main project or 2 additional subjects. Plaque sampling on the two test subjects will be for calibration purposes, to ensure the sampling technique yields samples with sufficient volume to reliably extract bacterial DNA.

Patient Participation:

Test Sample Collection (2 subjects):

- 1/Consent form and Eligibility review
- 2/Questionnaire
- 3/Examination and diagnosis for root surface caries (photographs when possible)
- 4/Bacterial sample collection

1st appointment:

- 1/Consent form and Eligibility review
- 2/Questionnaire
- 3/Examination and diagnosis for root surface caries (Pre-SDF photographs when possible)
- 4/Bacterial sample collection
- 5/SDF application
- 6/Post-SDF application photograph

2nd appointment (one month recall):

- 1/Questionnaire

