- 2/Examination and diagnosis for root or cervical surface caries to confirm if caries still exist (Photographs when possible)

3/Bacterial sample collection

Outcome Measures and its Assessment:

Patients will be seen twice, at baseline and at one-month recall, to compare the microbial composition of bacterial samples at the two different stages. Also, questionnaires will be completed by the patients at baseline and after one month to collect information on tooth brushing behavior, use of fluoride toothpaste, frequency of sweet snack intake between meals. Patients will also be asked about the acceptability of the treatment. Two eligible subjects with multiple eligible lesions will be seen for plaque collection calibration to ensure the plaque sample technique yields adequate volume to extract bacterial DNA for analysis. These subjects can also participate in the baseline and one-month recall, if the subject elects.

Incentives:

1/Participants will be given a toothbrush and toothpaste at the initial visit, and \$10 for their initial participation. We will pay for patient parking for the visit.

2/Fifteen dollars at the one-month recall research clinical visit. We will pay for patient parking at the visit.

3/At the one month recall, if active caries still exists or if the patient does not like the color, patients will be offered an appropriate restoration at our expense at the General Dentistry Clinic at the University of Michigan.

4/Two subjects will also participate in a test plaque sample collection visit. These subjects will receive \$18 for this visit and will receive compensation for patient parking.

Collection and determination of the bacteria involved in the carious lesions:

Gracey curettes will be used to collect plaque samples. Plaque samples will be coded, which will allow the samples to be connected to the overall study data. These samples will be used to identify the types of bacteria involved in the carious lesions and bacteria arrested after the application of the testing material after one month. The microbial composition of the samples will be assessed using human oral microbe identification microarray (HOMINGS). After the bacterial collection, the samples from the cervical or root carious lesions will be suspended in tubes containing 150 µl of TE (Tris, EDTA) Buffer. The bacterial samples will be stored at -80 °C. Prior to shipment to Forsyth for HOMINGS analyses, genomic DNA will be

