purified using the Master Pure Gram Positive DNA Purification kit (Epicentre Biotechnologies, Madison, WI, USA), with modifications (<http://mim.forsyth.org>). DNA samples will be sent on dry ice to Forsyth Institute. Per Forsyth Institute and the University of Michigan Office of Technology Transfer, a Material Transfer Agreement (MTA) will not be required prior to sharing of the samples.

HOMINGS:

At the Forsyth Institute, microbial profiles will be generated from image files of scanned HOMINGS microarrays (<https://homings.forsyth.org>). In brief, concentration levels of approximately 600 oral taxa will be determined by microarray hybridization using a fluorescent readout reverse-capture method.³⁶

Fluorescently labeled sample microbial DNA will be captured by 16S rRNA-based probes attached to glass slides. The fluorescent intensity for each probe will be scanned, normalized and scaled as previously reported.³⁶ Signals of 2× backgrounds will be considered to be negative and assigned a HOMINGS level score of 0. Positive hybridization signals will be categorized into five levels, with 1 indicating a signal that was just detectable, and 5 indicating maximum signal intensity.³⁷

Statistical Analysis:

Data will be analyzed using SPSS Pc+ version 22.0 statistical software. Descriptive statistics (mean, standard deviation, frequencies and percentages) will be used to describe the quantitative and categorical variables. Appropriate parametric statistical tests (one way analysis of variance followed by Tukey's test) and non-parametric statistical tests (Pearson's chi-square and Krushal Wallis test) will be used depending on the type and distribution of variables. A p-value ≤ 0.05 will be used to report the statistical significance of results.

Future Research:

Data and any samples remaining following HOMINGS analysis may be retained for future analysis/research. Subjects will provide or deny permission for their samples and data from this project to be used in future research in the informed consent document.

References:

1. Petersen PE, Yamamoto T: Improving the oral health of older people: the approach of the WHO global oral health programme. *Community Dent Oral Epidemiol* 2005; 33:81–92.

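### The main comparison is before/after in the same 20 participants, but the plan names only independent-group tests, which lose power if a participant's two samples are positively correlated

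*Combined protocol and SAP*

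**What the plan says.** The design is a single group measured twice. The Objective section describes "assessing microbial deposits on root or cervical caries lesions before and 1 month after SDF application". Under Sample Size, "A sample including 20 subjects is decided to constitute the study sample", and "Samples will be collected from each patient at the first visit and at the one month recall visit". The Treatment section takes plaque from one randomly chosen eligible lesion per person. The Outcome Measures section gives the purpose of the two visits: "Patients will be seen twice, at baseline and at one-month recall, to compare the microbial composition of bacterial samples at the two different stages". The section on collecting and determining the bacteria confirms that samples can be linked: "Plaque samples will be coded, which will allow the samples to be connected to the overall study data".

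The Statistical Analysis section names the tests: "Appropriate parametric statistical tests (one way analysis of variance followed by Tukey's test" on the parametric side and, on the non-parametric side, Pearson's "chi-square and Krushal Wallis test) will be used depending on the type and distribution of variables". The threshold is p ≤ 0.05, with sidedness not stated. The HOMINGS section defines the outcome as a score from 0 to 5 for each of about 600 taxa.

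**The concern.** Each participant supplies both a baseline and a one-month sample, so the two sets of 20 values are matched. One-way ANOVA, Kruskal-Wallis and Pearson's chi-square treat them as 40 unrelated observations. The rule for choosing among them looks at the type and distribution of the variable and not at pairing, so following it does not lead to a paired test. Tukey's test adds nothing when only two time points are compared.

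Two plaque samples from one mouth are plausibly positively correlated. If they are, these tests use too large a standard error. They become conservative, and a real shift after SDF is more likely to be missed. With 20 participants, no control arm and no stated power calculation, a null result could then reflect the test and not the agent. If the correlation were negative, the error would run the other way and false positives would exceed 5%.

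**Working it through.** **Inputs from the documents.** 20 participants and two samples each (Sample Size); one lesion per person (Treatment); significance at 0.05 and the named tests (Statistical Analysis); score 0-5 (HOMINGS). The plan gives no effect size, SD, power, correlation or dropout, so there is no sample-size calculation to reproduce.

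**Assumptions.** Two-sided 5%, 20 complete pairs, equal SDs at both visits, and a within-person correlation ρ that is varied.

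**Mechanism.** The variance of the mean change is 2σ²(1 − ρ)/n. The independent-group tests use 2σ²/n. Their standard error is therefore too large by 1/√(1 − ρ): 1.20, 1.41 and 1.83 at ρ = 0.3, 0.5 and 0.7.

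**1. ANOVA against the paired t-test.** With n = 20 pairs, the noncentral t (19 df) gives 80% power at 0.66 SD of the differences. In units of the raw SD this is 0.66 × √(2(1 − ρ)), which is 0.78, 0.66 and 0.51 at ρ = 0.3, 0.5 and 0.7. Simulating bivariate normal data gives:

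| ρ | Paired t power | ANOVA power | ANOVA type I error |
|---|---|---|---|
| 0 | 80% | 82% | 5.1% |
| 0.3 | 80% | 70% | 2.1% |
| 0.5 | 80% | 54% | 0.7% |
| 0.7 | 80% | 26% | 0.1% |

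At ρ = -0.2 the ANOVA type I error is 7.3%.

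The raw shift changes from row to row, so the same comparison is also given at a constant raw shift of 0.6 SD. At ρ = 0.3 / 0.5 / 0.7, ANOVA has 45% / 44% / 43% power and the paired t-test 58% / 72% / 91%.

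**2. Kruskal-Wallis against signed-rank on the 0-5 score.** A normal latent variable is cut into six levels and shifted by 0.6 SD, with correlation on the latent scale and tie-corrected tests.

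| Baseline scores | Test | ρ = 0.3 | ρ = 0.5 | ρ = 0.7 |
|---|---|---|---|---|
| Six equally likely levels | Kruskal-Wallis | 41% | 39% | 38% |
| | Signed-rank | 51% | 62% | 81% |
| Half at 0, 10% at each of 1-5 | Kruskal-Wallis | 33% | 31% | 28% |
| | Signed-rank | 39% | 47% | 62% |

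At ρ = 0 the two tests are within 3 points of each other.

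**3. Chi-square against McNemar for detected/not detected.** All paired 2×2 tables with n = 20 are enumerated exactly, with latent correlation ρ.

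| Detection | Test | ρ = 0.3 | ρ = 0.5 | ρ = 0.7 |
|---|---|---|---|---|
| 70% to 40% | Chi-square | 46% | 46% | 45% |
| | McNemar, mid-p | 51% | 57% | 65% |
| | McNemar, asymptotic | 51% | 59% | 71% |
| 90% to 60% | Chi-square | 63% | 64% | 64% |
| | McNemar, mid-p | 61% | 66% | 72% |
| | McNemar, asymptotic | 65% | 72% | 81% |

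At ρ = 0 chi-square is slightly ahead of asymptotic McNemar (62% against 57% for 90% to 60%). The highest chi-square type I error is 3.3% / 2.1% / 1.0% at ρ = 0.3 / 0.5 / 0.7, and 6.7% at -0.2. Over nine detection rates from 0.2 to 0.95 and ρ from -0.3 to 0.7, type I error is at most 4.3% for mid-p McNemar, 4.9% for asymptotic McNemar and 2.4% for exact McNemar.

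**The case against.** - **The wording leaves room.** The section asks for appropriate tests, and a one-way repeated-measures ANOVA on two time points equals a paired t-test. That is possible for ANOVA alone. Kruskal-Wallis and Pearson's chi-square have no paired reading, and the listed companions point to independent groups.
- **The tests may be meant for other data**, such as questionnaire answers or DMFT, where Tukey's test could be used across three or more categories. This limits the Tukey point to the two-time-point comparison. It does not help the main analysis, which would then have no named test.
- **The harm depends on an unstated correlation.** This stands. The plan does not even say outright that the same lesion is sampled at recall, although the samples are paired by person either way. With positive correlation the error is towards missed effects, not false claims. The loss is not uniform: at ρ = 0.3 and detection falling from 90% to 60%, mid-p McNemar is slightly below chi-square.
- **The fall to 26% is easily misread.** It reflects a raw shift that shrinks as ρ rises. At a fixed raw shift ANOVA stays near 44%, and the paired test pulls away from it.
- **Multiplicity.** If all 600 taxa were tested and null, restoring a true 5% level at ρ = 0.5 would raise expected false positives from about 4 (600 × 0.7%) to 30 (600 × 5%). That is a separate gap to be handled alongside this one. It is not a reason to keep a test that ignores the pairing.

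**Conclusion.** The point holds, and the analysis is wrong as written. It is not merely short of detail: the only hypothesis test is a within-person contrast, and every named test assumes independent groups. The named tests keep their nominal level only if two samples from one mouth are uncorrelated, which the plan neither states nor supports.

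The size is illustrative because the correlation, the effect and complete follow-up of all 20 are assumed. At a correlation of 0.5, ANOVA's power is 26 points below the paired t-test's 80%, and Kruskal-Wallis is 16 to 23 points below signed-rank in the two score distributions examined. For detection data at that correlation, chi-square is 2 to 13 points below McNemar, depending on the version and the detection rates. There is no material harm at zero correlation. It should be corrected before the data are analysed.

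**What to change.** In the Statistical Analysis section, for the baseline versus one-month comparison:

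- Name the Wilcoxon signed-rank test, or a paired t-test on transformed levels, for taxon scores.
- Name a McNemar test for detected/not detected and state the version, asymptotic or mid-p. The exact version is very conservative with 20 pairs.
- Delete Tukey's test from this comparison.
- Keep ANOVA, Kruskal-Wallis and chi-square only for comparisons between participants.

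The cost is a few words. No extra visits, samples or data are needed, because samples are already coded to the study data, and both McNemar versions use only the two discordant counts.

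### No result is tied to H_0, and if taxa are tested individually the only rule for about 600 scored taxa is p ≤ 0.05, with nothing said about adjustment across them

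*Combined protocol and SAP*

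**What the plan says.** All references are to the combined protocol and SAP.

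- **Hypothesis** sets one global H_0, that 38% SDF does not inhibit bacteria. It attaches no taxon, index or statistic to it.
- **Outcome Measures and its Assessment** says patients are seen twice "to compare the microbial composition of bacterial samples at the two different stages". No primary variable or summary is named.
- **Collection and determination of the bacteria involved in the carious lesions** gives this purpose for the sampling: "identify the types of bacteria involved in the carious lesions and bacteria arrested after the application of the testing material after one month".
- **HOMINGS** says "concentration levels of approximately 600 oral taxa will be determined by microarray hybridization". Weak signals are "considered to be negative and assigned a HOMINGS level score of 0", and positive signals fall into five levels, so each taxon has a score from 0 to 5.
- **Introduction** describes the same technology differently, as one that "utilizes the speed and efficiency of next generation sequencing", and adds: "Nearly 600 oral bacterial taxa are identified at the Species-level and Genus-level identification of remaining sequences for 129 genera".
- **Sample Size** gives 20 subjects, each sampled at baseline and at one month.
- **Statistical Analysis** names one-way ANOVA with Tukey's test, Pearson's chi-square and "Krushal Wallis test) will be used depending on the type and distribution of variables". It then sets the threshold: "A p-value ≤ 0.05 will be used to report the statistical significance of results".

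**The concern.** There are two gaps.

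First, nothing says which result decides H_0. One taxon falling, another rising, or any p-value at or below 0.05 could each be presented as rejecting it. This is an omission in the text and needs no assumption.

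Second, naming the bacteria that were arrested calls for decisions taxon by taxon, and the only decision rule offered is p ≤ 0.05. Tukey's test does not help. It adjusts comparisons between group means within one variable, and two visits give only one comparison per taxon.

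If taxa are tested individually, the study could list bacteria as reduced when nothing changed between visits, and the list could then be read as SDF's mechanism of action.

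**Working it through.** **The plan's own figures.** The only design figures are 20 subjects and p ≤ 0.05. No effect size, standard deviation, power or dropout is given, so 20 cannot be reproduced. No error rate across taxa is stated.

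**Step 1: nominal arithmetic.** Suppose m taxa are tested, each test truly has 5% error, and half of the errors are decreases. Then the expected number of false results is 0.05m, and with independent taxa P(at least one false decrease) = 1 − 0.975^m.
- m = 20: 1 expected false result; 1 − 0.975^20 = 0.40
- m = 100: 5 expected; 1 − 0.975^100 = 0.92
- m = 600: 30 expected, 15 of them decreases; probability above 0.999

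These figures do not describe the plan's named tests, which treat the two visits as independent groups. With positive correlation between visits, those tests overstate the variance of the difference, and their real error falls below 5%.

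**Step 2: the named Kruskal-Wallis test under no change.** From the documents: 20 pairs, 0-5 scores, threshold 0.05. Assumed: a latent normal variable per taxon, correlation r between visits, between-taxon correlation 0 to 0.6, detection spread over 20-80%, and levels 1-5 equally likely when detected. Simulation used 2,000 runs for 20 and 100 taxa and 1,000 for 600. Chance of at least one false decrease:

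| Taxa tested | r = 0.3 | r = 0.5 | r = 0.7 | r = 0.9 |
|---|---|---|---|---|
| 20 | 13-23% | 9-12% | 3-4% | 0.2-0.3% |
| 100 | 36-73% | 21-47% | 11-16% | about 1% |
| 600 | 54-100% | 42-97% | 31-65% | 5-7% |

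The range in each cell comes from the between-taxon correlation. None of these values is a bound. With sparser detection (2-50%, between-taxon correlation 0-0.3), 100 taxa give 56-74%, 23-25% and 3% at r = 0.3, 0.7 and 0.9. If the readout is continuous and one-way ANOVA is used, 100 independent taxa give 65%, 31%, 4.6% and 0.0% across the four columns.

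**Step 3: paired tests, still unadjusted.** An exact signed-rank test at 0.05 under the same model (500-800 runs, r = 0.3 to 0.9) gives 13-36% for 20 taxa and 34-90% for 100. High r no longer protects. With Benjamini-Hochberg at 5% on these tests, the chance of any false taxon is 0-3.4%.

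**Step 4: what adjustment costs.** Here 20 of 100 taxa are truly reduced by 1 latent SD, detection is 2-80%, between-taxon correlation is 0.3, and there are 200 runs per r. The filter requires detection in at least 10 of the 40 samples. True taxa found, of 20:

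| Method | r = 0.3 | r = 0.7 | r = 0.9 |
|---|---|---|---|
| Unadjusted Kruskal-Wallis | 10.7 | 11.7 | 12.0 |
| Paired, Benjamini-Hochberg, no filter | 2.4 | 6.5 | 9.1 |
| Paired, Benjamini-Hochberg, with filter | 3.1 | 7.2 | 9.6 |

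The share of flagged taxa that are false is 15%, 2.5% and 0.1% for unadjusted Kruskal-Wallis, and 1-2% with Benjamini-Hochberg. The filter adds 0.7, 0.7 and 0.5 taxa. When detection is 20-80% it adds essentially nothing (4.1, 9.8 and 12.4 without it; 4.3, 9.9 and 12.3 with it).

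**The case against.** The strongest reply is that the plan never says each taxon will be tested and never says results will be unadjusted. Its outcome is microbial composition and its H_0 is global. One community-level comparison would fit both and raise no multiplicity across taxa. The arrested bacteria could be reported descriptively, since means, frequencies and percentages are also planned. This stands as a limit on the second gap. It does not touch the first, because no such comparison is named.

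A second reply is that the risk spans almost the whole range from zero to certainty, on inputs the documents do not give, and is already below about 5% in some cases. This also stands. A reader might infer that testing some 600 taxa at 0.05 makes false findings practically certain. The documents do not support that: the number of taxa to be tested is not stated, and the named tests have real error below 5% when visits are positively correlated.

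Third, a reader might infer that adjustment beats the plan throughout. It does not. At r = 0.9 the unadjusted unpaired test finds more true taxa (12.0 against 9.6) with a smaller false share (0.1% against 1-2%). The fall in false share is clear only at low r, and there the loss of true findings is greatest.

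Finally, this is a small single-arm study, and it may be argued that calling the taxon results exploratory would be enough. But the text does not call them exploratory; it states H_0, H_A and a significance threshold.

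**Conclusion.** The concern holds in this form: no result is tied to H_0, and if taxa are tested individually, as the aim of identifying arrested bacteria implies, the plan has no rule for separating chance changes from real ones. The omission is certain; the size of its consequence is conditional on the number of taxa tested and on r.

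Under the stated model with Kruskal-Wallis and 100 taxa, the chance of a false decrease runs from 36-73% at low correlation to about 1% at r = 0.9. For 20 taxa at r of 0.7 or more it is below about 5%. The low values are an accident of using unpaired tests on paired data and disappear once the tests are paired.

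The main gain from a change is therefore a defined test of H_0, and error control that does not rely on that accident. The plan should be amended before data are seen. The unpaired tests themselves, and the lack of a control group when everyone also receives oral hygiene instruction, are separate issues; the null tested here is only no change between visits.

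**What to change.** Before any data are seen, replace the blanket threshold in Statistical Analysis with two rules. First reconcile the readout: the Introduction describes sequencing and the HOMINGS section describes microarray levels, and the summary and tests depend on which applies.

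1. **Primary test.** Name one paired test of H_0 at two-sided 0.05 on a single pre-specified directional summary, chosen by the sponsor. A score over a fixed species list is one option, but it narrows H_A to those species and the plan should say so. If the data are relative abundances, the total over all taxa is fixed and cannot show a decrease.
2. **Individual taxa, if tested.** Use paired tests with Benjamini-Hochberg at a 5% false discovery rate. Report q-values and direction for every taxon tested, and label these results exploratory. A detection filter is optional. If used, it should pool both visits and ignore change between them; its gain is at most about 1 taxon of 20 when many taxa are sparse, and nil at 20-80% detection.

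No new samples or visits are needed. The cost is sensitivity per taxon: in the simulation above, about 3, 7 and 9-10 of 20 true taxa are found with the filter at r = 0.3, 0.7 and 0.9, against about 11-12 for unadjusted Kruskal-Wallis. For a paired t-test with 20 subjects and 80% power, the detectable change is 0.66 SD of the differences at 0.05, 0.84 SD at 0.01 and 1.15 SD at 0.0005 (0.05/100). The primary test keeps the 0.05 level and pays none of this.
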